**Table 8-1. List of Items on the HIVTSQ**

Question	Response Options for Status Form	Response Options for Change Form	Subscale
How satisfied are you with your current treatment?	Very satisfied 6 to 0 very dissatisfied	Much more satisfied now 3 to 3 much less satisfied now	General Satisfaction/Clinical
How well controlled do you feel your HIV has been recently?	Very well controlled 6 to 0 very poorly controlled	Much better controlled now 3 to 3 much worse controlled now	General Satisfaction/Clinical
How satisfied are you with any side effects of your present treatment?	Very satisfied 6 to 0 very dissatisfied	Much more satisfied now 3 to 3 much less satisfied now	General Satisfaction/Clinical
How satisfied are you with the demands made by your current treatment?	Very satisfied 6 to 0 very dissatisfied	Much more satisfied now 3 to 3 much less satisfied now	Lifestyle/Ease
How convenient have you been finding your treatment to be recently?	Very convenient 6 to 0 very inconvenient	Much more convenient now 3 to 3 much less convenient now	Lifestyle/Ease
How flexible have you been finding your treatment to be recently?	Very flexible 6 to 0 very inflexible	Much more flexible now 3 to 3 much less flexible now	Lifestyle/Ease
How satisfied are you with your understanding of your HIV?	Very satisfied 6 to 0 very dissatisfied	Much more satisfied now 3 to 3 much less satisfied now	Lifestyle/Ease
How satisfied are you with the extent to which the treatment fits in with your lifestyle?	Very satisfied 6 to 0 very dissatisfied	Much more satisfied now 3 to 3 much less satisfied now	Lifestyle/Ease
Would you recommend your present treatment to someone else with HIV?	Yes I would definitely recommend the treatment 6 to 0 No I would definitely not recommend the treatment	Much more likely to recommend the treatment now 3 to 3 much less likely to recommend the treatment now	General Satisfaction/Clinical
How satisfied would you be to continue with your present form of treatment?	Very satisfied 6 to 0 very dissatisfied	Much more satisfied now 3 to 3 much less satisfied now	General Satisfaction/Clinical

### **8.3.1. HIV Treatment Satisfaction Questionnaires Statistical Analysis Method**

The HIVTSQs scale and subscale totals at baseline, and the HIVTSQc scale and subscale totals at each visit will be summarized using descriptive statistics.

For each subscale, if more than 1 question is missing, then the subscale total or subscale total in change will be set to missing. Otherwise, the missing response will be imputed by taking the average of the non-missing responses from the other questions in that subscale.

For the scale total or scale total in change, if more than 5 questions are missing, then the value will be set to missing. Otherwise, the missing response(s) will be imputed by taking the average of the nonmissing responses from the other questions.

If two responses are provided for a single question, and the scores are next to each other, then the midpoint will be used. If two responses are provided for a single question, and the scores are not immediately next to each other, then the response will be considered missing.

### **8.4. Functional Assessment of Chronic Illness Therapy – Fatigue**

The Functional Assessment of Chronic Illness Therapy (FACIT) was adopted from the Functional Assessment of Cancer Therapy in 1997 as an instrument to measure the health related quality of life (HRQOL) of patients with chronic illnesses. FACIT-F contains 13 additional items not in the initial FACIT questionnaire under the heading “Additional Concerns” that comprise the fatigue subscale.

The Functional Assessment of Chronic Illness Therapy - Fatigue (FACIT-F) Version 4.0 is a 40 item, self-reported questionnaire which measures the HRQOL of patients with chronic illnesses over a one-week time interval. Each item takes a range of 0–4, corresponding to (0) Not at all; (1) A little bit; (2) Somewhat; (3) Quite a bit; (4) Very much. Forty individual items generate 5 subscales: (1) Physical Well-Being (PWB); (2) Social/Family Well-Being (SWB); (3) Emotional Well-Being (EWB); (4) Functional Well-Being (FWB); and (5) Fatigue Subscale (FS).

#### **8.4.1. Scoring the Functional Assessment of Chronic Illness Therapy – Fatigue**

Full details of the scoring of the FACIT-F are available in the initial publication. A brief overview appears below. Instructions for scoring each subscale are presented in the table below. If “Reverse item?” is “Yes”, then the response should be reversed by subtracting the response from “4” (ie, New response = 4 – original response).

Missing values will not be imputed. Prorating subscale scores is acceptable as long as more than 50% of items were answered (a minimum of 4 out of 7 items, 4 of 6 items, and 7 out of 13 items). This is done by multiplying the sum of the subscale by the number of items in the subscale, then dividing by the number of items actually answered.

**Table 8-2. Items by Subscale and Scoring Algorithm for FACIT-F**

Subscale	Item Code	Reverse item?	Scoring Algorithm
PWB	GP1	Yes	Sum individual item score → Multiply by 7 → Divide by the number of answered items (Score range: 0–28)
	GP2	Yes	
	GP3	Yes	
	GP4	Yes	
	GP5	Yes	
	GP6	Yes	
	GP7	Yes	
SWB	GS1	No	Sum individual item score --> Multiply by 7 ---> Divide by the number of answered items (Score range: 0–28)
	GS2	No	
	GS3	No	
	GS4	No	
	GS5	No	
	GS6	No	
	GS7	No	
EWB	GE1	Yes	Sum individual item score → Multiply by 7 → Divide by the number of answered items (Score range: 0–24)
	GE2	No	
	GE3	Yes	
	GE4	Yes	
	GE5	Yes	
	GE6	Yes	
FWB	GF1	No	Sum individual item score → Multiply by 7 → Divide by the number of answered items (Score range: 0–28)
	GF2	No	
	GF3	No	
	GF4	No	
	GF5	No	
	GF6	No	
	GF7	No	

Subscale	Item Code	Reverse item?	Scoring Algorithm
FS	HI7	Yes	Sum individual item score → Multiply by 13 → Divide by the number of answered items (Score range: 0–52)
	HI12	Yes	
	An1	Yes	
	An2	Yes	
	An3	Yes	
	An4	Yes	
	An5	No	
	An7	No	
	An8	Yes	
	An12	Yes	
	An14	Yes	
	An15	Yes	
	An16	Yes	

PWB Physical Well Being; SWB Social/Family Well Being; EWB Emotional Well Being; FWB Functional Well Being; and FS Fatigue Subscale.

Three aggregate scores can be computed as shown in [Table 8-3](#), subject to the requirements listed:

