## 8. PATIENT REPORT OUTCOMES

The Patient reported outcomes (PROs) include: (1) Visual Analogue Scale (VAS) adherence questionnaires; (2) Short Form-36 Version 2 Health Survey (SF-36); (3) HIVTSQs Status version (at Day 1 only)/HIVTSQc Change version (post-Day 1); (4) FACIT-F; (5) EQ-5D. Unless otherwise stated, multiple responses and out of range responses will be set to missing and missing responses will not be imputed. The Safety Analysis Set will be used in all analyses. No inferential statistics will be provided. All reported data will be listed.

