**Table 8-3. Computation of Aggregate Scores**

Aggregate Score	Formula	Requirement
FACIT-F Trial Outcome Index (TOI)	PWB+FWB+FS	PWB, FWB, FS all nonmissing
FACT-G total score	PWB + SWB + EWB + FWB	At least 80% nonmissing (ie, 22 out of 27)
FACIT-F total score	PWB + SWB + EWB + FWB + FS	At least 80% nonmissing (ie, 33 out of 40)

FACIT F Functional Assessment of Chronic Illness Therapy Fatigue; PWB Physical Well Being; SWB Social/Family Well Being; EWB Emotional Well Being; FWB Functional Well Being; and FS Fatigue Subscale.

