**Table 8-4. Scores of EQ-5D-3L Descriptive System**

Original Response Category	Score
No problems	1
Some problems	2
Extreme problems	3

Note: Missing values is to be coded as 9. Ambiguous values (eg, 2 boxes are ticked for a single dimension) should be treated as missing values.

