### 8.5.2. EQ-5D Single Summary Index

EQ-5D health states, defined by the EQ-5D descriptive system, will be converted into a single summary index using the UK time trade-off (TTO) value set ([Appendix 3](#)). For example, the health state is 11111 if the response to each of the 5 dimensions of the EQ-5D system is 1. Since there are 3 possible responses (ie, 1, 2 and 3) to each of the 5 dimensions of the EQ-5D system, there are  $3^5 = 243$  health states in total.

For the UK TTO value set, the index is calculated for each of the health states (see [Appendix 3](#) for details). Missing responses for EQ-5D-3L Questionnaire will not be imputed. If any one of the 5 dimensions is missing, the index will be missing.

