33) Lipid modifying medication analyses:

- Lipid modifying medication is defined to be the concomitant medication with any concomitant medication class “LIPID MODIFYING AGENTS” and CMDECOD contains wording of “STATIN” in the ADCM dataset.

- Subjects who took lipid modifying medications at study entry refer to the subjects who use of the lipid modifying agents at study day 1 (ie, the first dose date). More specifically, subjects with “Lipid Modifying Agent Use at Study Entry” include those subjects in Safety Analysis Set with: 1) any selected CM record with the start date  $\leq$  the first dose date, and 2) the end date of the selected CM record is ongoing or the end date of the selected CM record  $\geq$  the first dose date.
- Subjects who initiated lipid modifying medications during the study include the subjects in the Safety Analysis Set who didn’t take lipid modifying medications at study entry and met the following criteria: 1) for subjects who permanently discontinued study drug with any selected CM record started after the first dose date and on and prior to the last dose date; 2) for subjects who are still on study drug with any selected CM records started after the first dose date.
- For lipid modifying medications with the start date completely unknown, we assume the start date is on or before the first dose date, lipid modifying medication was considered as being taken at study entry if the end date is not prior to the first dose date (ie, the end date is on or after the first dose date, completely unknown, or ongoing).
- Lipid modifying medications with the start date prior to the first dose date and the end date completely unknown were considered as being taken at study entry.

34) Age for laboratory test reference range will be based on the age at the sample collection date.

35) For figures, if at a visit where n (sample size) for any treatment group  $< 5$ , data for that treatment group will not be displayed at the visit in figure, but all data will be included in the corresponding table summary.

36) For the PRO data, data up to 30 day after the last dose date for subjects who permanently discontinued of study drug will be summarized.

37) For PRO data, unless otherwise stated, multiple responses and out of range responses will be set to missing and missing responses will not be imputed.

Out of range value is determined based on the following table for within-range response values:

SF-36v2 Health Survey:

Question	Response	

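### SAP Table 8-2 multiplies the six-item FACIT-F Emotional Well-Being subscale by 7 instead of 6; programmed as written, every non-zero score is one sixth too high

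*SAP*

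**What the plan says.** SAP section 8.4 scores each FACIT-F item 0 to 4. Table 8-2 then gives one row per subscale with its items, which of them are reversed, and a formula. The EWB row lists six items, GE1 to GE6, and instructs the analyst to sum them and then "Multiply by 7 → Divide by the number of answered items (Score range: 0–24").

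Section 8.4.1 describes the same step in words: prorate by "multiplying the sum of the subscale by the number of items in the subscale", then divide by the number answered. It sets the completeness requirement at "a minimum of 4 out of 7 items, 4 of 6 items, and 7 out of 13 items". It also points to the table for the scoring of each subscale.

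Table 8-3 builds the totals. FACT-G is the sum of the four well-being subscales and requires "At least 80% nonmissing (ie, 22 out of 27"). The FACIT-F total adds the Fatigue Subscale and counts 40 items. The Trial Outcome Index uses Physical Well-Being, Functional Well-Being and Fatigue only. Section 8.4.2 commits to descriptive summaries of every subscale and aggregate score at each visit, overall and by Part, plus a by-subject listing.

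For the EQ-5D, the note to Table 8-4 says "Missing values is to be coded as 9", and section 8.5.2 says "If any one of the 5 dimensions is missing, the index will be missing". Section 8 has a general rule for all questionnaires that "multiple responses and out of range responses will be set to missing". Appendix 5 item 37 repeats that rule and adds "Out of range value is determined based on the following table for within-range response values", but the tables that follow cover only the SF-36 and the VAS adherence questionnaire.

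**The concern.** The EWB row contradicts itself: six items scored 0 to 4, multiplied by 7 and divided by the number answered, cannot have a maximum of 24. It also contradicts the prose rule in section 8.4.1. The multiplier applies to every form, not only to forms with missing items, so a fully completed questionnaire is also inflated.

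At stake are the reported EWB, FACT-G and FACIT-F total scores at each visit. An error of this kind can pass unnoticed, because most inflated scores still lie inside the printed range.

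The EQ-5D point is separate and weaker. The index code in Appendix 5 item 38 returns a missing index only when a dimension holds the SAS missing value. If a response coded 9 reached that step without being recoded, the code would return a number where section 8.5.2 requires a missing value.

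**Working it through.** **Inputs.** Item scores are 0 to 4 (SAP section 8.4); reversal is 4 minus the response (section 8.4.1), so reversed items are also 0 to 4. EWB has six items, multiplier 7 and stated range 0–24 (Table 8-2). At least four of the six must be answered (section 8.4.1). Let S be the sum over the n items answered, so the maximum of S is 4n.

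**The plan's stated range.** Under section 8.4.1 the score is S × 6 / n:
- n = 6: 24 × 6 / 6 = 24
- n = 5: 20 × 6 / 5 = 24
- n = 4: 16 × 6 / 4 = 24

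This reproduces 0–24.

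**The table as written.** The score is S × 7 / n:
- n = 6: 24 × 7 / 6 = 28
- n = 5: 20 × 7 / 5 = 28
- n = 4: 16 × 7 / 4 = 28

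The range is 0–28 at every permitted level of completeness.

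**Which element is wrong.** The same check on all five rows of Table 8-2:

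| Subscale | Items | Multiplier | Stated maximum | Maximum as written |
|---|---|---|---|---|
| Physical | 7 | 7 | 28 | 28 |
| Social/Family | 7 | 7 | 28 | 28 |
| Emotional | 6 | 7 | 24 | 28 |
| Functional | 7 | 7 | 28 | 28 |
| Fatigue | 13 | 13 | 52 | 52 |

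Only the EWB row fails. The item counts in Table 8-3 also require six EWB items: 7 + 7 + 6 + 7 = 27, and 27 + 13 = 40. So the multiplier is the error, not the range or the item list.

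**Size.** The ratio is (S × 7 / n) / (S × 6 / n) = 7/6 for every non-zero S and every n; a score of 0 stays 0. The excess is one sixth of the true EWB score. On complete forms:
- 6 becomes 7; 12 becomes 14; 18 becomes 21
- 20 becomes 20 × 7 / 6 = 23.33, still inside 0–24
- 21 becomes 24.5, the first value outside the range; 24 becomes 28

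True scores of 1 to 20 therefore stay within the printed range, and only 21 to 24 exceed it.

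**Totals (maximum values).**
- FACT-G: 28 + 28 + 24 + 28 = 108; as written 28 + 28 + 28 + 28 = 112
- FACIT-F total: 108 + 52 = 160; as written 112 + 52 = 164
- Trial Outcome Index: 28 + 28 + 52 = 108, unchanged

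**EQ-5D code with an unrecoded 9.** The minus signs are absent from the code as extracted. I read each term as a subtraction, which agrees with the negative constant and the printed index values in SAP Appendix 3. A 9 matches neither level 2 nor level 3, but it is not equal to 1, so it triggers the constant of 0.081.
- 9-1-1-1-1: 1 − 0.081 = 0.919. Against a baseline of 11111 (index 1.000) the change is −0.081, which Table 8-5 classes as worsening because it is at or below −0.07.
- 9-2-1-1-1: 1 − 0.104 − 0.081 = 0.815, the printed value for 12111. Here the missing item is in effect scored as level 1.

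**The case against.** The strongest reply is that this is a slip which the SAP itself resolves. The prose rule, the item list, the printed range and the item counts in Table 8-3 all point to 6. Section 8.4.1 also calls its text a brief overview and refers to the initial publication for full scoring, so a careful programmer might never use the 7. That is fair, and it is why the harm is conditional. It does not remove the conflict: the same section names the table as the place for subscale instructions, and SAP section 9 lists no FACIT publication to consult.

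A second reply is that the error would show up. Section 8.4.2 requires the maximum at every visit and a listing, so one complete form with a true score of 21 to 24 would put a value above 24 in print. On complete forms, 20 of the 24 non-zero scores would also become fractions, since only 6, 12, 18 and 24 stay whole. This part stands: detection is possible. It is not assured, because Appendix 5 item 10 reports summaries to the precision of the raw data, which could round the fractions away, and the documents give no EWB distribution from which to judge how often scores exceed 20.

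A third reply is that FACIT-F appears in no objective or endpoint and has no inferential analysis. That is correct, and it limits the importance of the point.

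On the EQ-5D, the intended result is explicit in section 8.5.2 and again in Appendix 3, and the general out-of-range rule may well catch a 9. Nothing in the documents shows that a 9 reaches the code. The point therefore remains a clarification.

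**Conclusion.** The concern holds. The EWB row of Table 8-2 is wrong as written: it yields 0–28 where the plan states 0–24, and the correct multiplier is 6. If it is programmed literally, every non-zero EWB score is too high by exactly one sixth, and the FACT-G and FACIT-F totals are too high by up to 4 points. This rests on one assumption, that the programmer follows the table rather than the prose of section 8.4.1. The consequence is limited to descriptive patient-reported output, so the correction should be made but does not bear on the trial's efficacy or safety conclusions.

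The EQ-5D remark is secondary. It applies only if a code of 9 is not recoded before the index is computed. The documents give no frequency of missing items, so the examples show the mechanism and not the size of any effect.

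**What to change.** In the EWB row of SAP Table 8-2, replace the multiplier 7 with 6. This aligns the row with its own range, with section 8.4.1 and with Table 8-3. Confirm which multiplier the scoring program uses and, if it is 7, rerun the EWB, FACT-G and FACIT-F total summaries and listings.

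As a clarification in Appendix 5 item 38, set the index to missing whenever any dimension is not 1, 2 or 3. This enforces what section 8.5.2 already requires, whether a missing response arrives as 9 or as the SAS missing value.

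The edits themselves are one digit and one line of code. If the SAP is already final, its section 1 requires the change to be documented in the clinical study report, so the cost is that note plus the program check. Neither change has a statistical downside.

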**Table 8-3. Computation of Aggregate Scores**

Aggregate Score	Formula	Requirement
FACIT-F Trial Outcome Index (TOI)	PWB+FWB+FS	PWB, FWB, FS all nonmissing
FACT-G total score	PWB + SWB + EWB + FWB	At least 80% nonmissing (ie, 22 out of 27)
FACIT-F total score	PWB + SWB + EWB + FWB + FS	At least 80% nonmissing (ie, 33 out of 40)

FACIT F Functional Assessment of Chronic Illness Therapy Fatigue; PWB Physical Well Being; SWB Social/Family Well Being; EWB Emotional Well Being; FWB Functional Well Being; and FS Fatigue Subscale.

#### 8.4.2. Functional Assessment of Chronic Illness Therapy – Fatigue Analysis Method

Scores for each subscale and aggregate score will be summarized overall and by Parts 1 and 2 for each visit using descriptive statistics (n, mean, SD, median, Q1, Q3, minimum and maximum).

A by-subject listing for the scores for each subscale and aggregate score will be provided by subject ID number and visits in chronological order.

#### 8.5. EQ-5D-3L

The EQ-5D-3L consists of the EQ-5D descriptive system and the EQ visual analogue scale (EQ VAS). The EQ-5D-3L descriptive system comprises the following 5 dimensions: mobility, self-care, usual activities, pain/discomfort and anxiety/depression. Each dimension has 3 levels: no problems, some problems, extreme problems. The EQ VAS records the respondent’s self-rated health on a vertical, visual analogue scale from 0 (“Worst imaginable health state”) to 100 (“Best imaginable health state”). This information can be used as a quantitative measure of health outcomes as judged by the individual respondents {[Rabin 2011](#)}.

##### 8.5.1. Scoring the EQ-5D-3L Descriptive System

The scores of EQ-5D-3L descriptive system are described in [Table 8-4](#).

**Table 8-4. Scores of EQ-5D-3L Descriptive System**

Original Response Category	Score
No problems	1
Some problems	2
Extreme problems	3

Note: Missing values is to be coded as 9. Ambiguous values (eg, 2 boxes are ticked for a single dimension) should be treated as missing values.

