### Appendix 3. UK TTO Value Set for EQ-5D-3L Questionnaire

For the UK TTO value set, the index is calculated for each of the health states based on the following equation:

Index 1 0.081 0.069 MO2 0.314 MO3 0.104 SC2 0.214 SC3 0.036 UA2  
0.094 UA3 0.123 PD2 0.386 PD3 0.071 AD2 0.236 AD3 0.269 N3

- -0.081 is a constant term for any dysfunctional state.
- MO2 is a dummy variable for level 2 of Mobility.
- MO3 is a dummy variable for level 3 of Mobility.
- SC2 is a dummy variable for level 2 of Self Care.
- SC3 is a dummy variable for level 3 of Self Care.
- UA2 is a dummy variable for level 2 of Usual Activities.
- UA3 is a dummy variable for level 3 of Usual Activities.
- PD2 is a dummy variable for level 2 of Pain/Discomfort.
- PD3 is a dummy variable for level 3 of Pain/Discomfort.
- AD2 is a dummy variable for level 2 of Anxiety/Depression.
- AD3 is a dummy variable for level 3 of Anxiety/Depression.
- N3 is a dummy variable that represents level 3 occurs within at least one dimension.

The index score is missing if any one of the 5 dimensions is missing.

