	Min	Max
1, 2, 4a to 4d, 5a to 5c, 6, 8, 9a to 9i, 10, 11a to 11d	1	5
3a to 3j	1	3
7	1	6

VAS adherence questionnaire:

Questions	Response	
	Min	Max
1	0	100
2	0	30
3	0	4

38) Computing EQ-5D index values with SAS using the UK TTO value set

The variables for the 5 dimensions of the EQ-5D descriptive system should be named 'mobility', 'selfcare', 'activity', 'pain', and 'anxiety'. The variable 'UK\_TTO' contains the values of the EQ-5D index.

You can copy and paste the syntax below directly into the SAS syntax window.

```
*****
* SAS syntax code for the computation of index *
* values with the UK MVH A1 TTO value set *
*****;

data Euroqol.Uk_data;
set Euroqol.EQ5D_states;

UK_TTO = 1;

if (mobility = 2) then UK_TTO = UK_TTO 0.069;
if (mobility = 3) then UK_TTO = UK_TTO 0.314;

if (selfcare = 2) then UK_TTO = UK_TTO 0.104;
if (selfcare = 3) then UK_TTO = UK_TTO 0.214;

if (activity = 2) then UK_TTO = UK_TTO 0.036;
if (activity = 3) then UK_TTO = UK_TTO 0.094;

if (pain = 2) then UK_TTO = UK_TTO 0.123;
if (pain = 3) then UK_TTO = UK_TTO 0.386;

if (anxiety = 2) then UK_TTO = UK_TTO 0.071;
if (anxiety = 3) then UK_TTO = UK_TTO 0.236;

if (mobility ne 1) or (activity ne 1) or (selfcare ne 1) or (pain ne 1) or
(anxiety ne 1) then UK_TTO = UK_TTO 0.081;
if (mobility = 3) or (selfcare = 3) or (activity = 3) or (pain = 3) or
(anxiety = 3) then UK_TTO = UK_TTO 0.269;

if (mobility = .) or (selfcare = .) or (activity = .) or (pain = .) or
(anxiety = .) then UK_TTO = . ;

output;
run;
```

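### Missing EQ-5D items are coded 9, but the printed SAS code recognises only `.` as missing, so an incomplete form would receive an index

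*SAP*

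**What the plan says.** - **Coding (SAP 8.5.1, Table 8-4).** Levels are scored 1, 2 and 3. For missing items, "Missing values is to be coded as 9". Ambiguous answers, such as two boxes ticked, "should be treated as missing values", so they also become 9.
- **Rule for the index (SAP 8.5.2).** "If any one of the 5 dimensions is missing, the index will be missing". The same section rules out imputing missing responses. SAP Appendix 3 repeats the rule: "The index score is missing if any one of the 5 dimensions is missing".
- **Code (SAP Appendix 5, item 38).** The SAS syntax is offered for direct use. Its constant is triggered by the condition beginning "if (mobility ne 1) or (activity ne 1) or (selfcare ne 1) or (pain ne 1) or". Its missing-data line begins "if (mobility = .) or (selfcare = .) or (activity = .) or (pain = .) or" and ends with "anxiety = .) then UK_TTO" being set to `.`. There is no branch for 9 and no recode step before it.
- **General rule for patient-reported outcomes (SAP section 8 and Appendix 5, item 37).** Out-of-range responses are set to missing unless something else is specified. Item 37 adds: "Out of range value is determined based on the following table for within-range response values". The tables that follow cover the SF-36 and the VAS adherence questionnaire only.
- **Use of the index (SAP 8.5.4, Table 8-5).** Change from baseline is summarised by visit. A fall of 0.07 or more counts as worsening and a rise of 0.07 or more as improvement.

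**The concern.** The coding instruction and the scoring code use different conventions for missing data, and no step joins them. A programmer who follows both as written breaks the SAP's own rule that an incomplete form has no index. Incomplete forms would then enter the index summaries as if they were observed health states. Some would also be counted as worsened or improved when the apparent change comes only from an unanswered item. Most of these values would look ordinary in a listing, because they coincide with legitimate entries in the value set.

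**Working it through.** **Inputs.** Decrements for levels 2 and 3 (SAP Appendix 3 and Appendix 5, item 38): mobility 0.069 / 0.314; self-care 0.104 / 0.214; usual activities 0.036 / 0.094; pain 0.123 / 0.386; anxiety 0.071 / 0.236. The constant is 0.081 and the level-3 term is 0.269. The minus signs missing from the extracted text are read as subtraction; they are not counted as an error.

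**Formula as coded.** Index = 1 − (sum of level-2 and level-3 decrements) − 0.081 if any item is not 1 − 0.269 if any item is 3. The index is then set to missing if any item is `.`.

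**Step 1: reproduce the plan's values.**
- 21111: 1 − 0.069 − 0.081 = 0.850 (printed 0.850).
- 11112: 1 − 0.071 − 0.081 = 0.848 (printed 0.848).
- 33333: 1 − (0.314 + 0.214 + 0.094 + 0.386 + 0.236) − 0.081 − 0.269 = −0.594 (printed −0.594).

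All 243 complete states match the printed table, so the code has been read correctly.

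**Step 2: count the incomplete patterns.** With four possible codes per item (1, 2, 3, 9), there are 4^5 − 3^5 = 1024 − 243 = 781 patterns with at least one 9. Under the printed code all 781 return a number and none is set to missing.

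**Step 3: what a 9 does.** It matches no level-2 or level-3 decrement, it satisfies the not-equal-to-1 condition, and it is not `.`. There are two cases:
- *Another item is at level 2 or 3.* The constant is already triggered, so the 9 counts simply as level 1. Pattern 29111 gives 1 − 0.069 − 0.081 = 0.850, the same as 21111. Pattern 39111 gives 1 − 0.314 − 0.081 − 0.269 = 0.336, the same as 31111. This covers 781 − 31 = 750 patterns.
- *All answered items are at level 1, or the form is blank.* The 9 itself triggers the constant, once per form. Patterns 11119 and 99999 both give 1 − 0.081 = 0.919. This covers 2^5 − 1 = 31 patterns. The highest printed value below 1.000 is 0.883 (state 11211), so 0.919 is not a valid index.

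**Step 4: effect on the responder categories.**

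| Baseline | Follow-up form | Index returned | Change | Category |
|---|---|---|---|---|
| 11111 = 1.000 | 11119 or blank | 0.919 | −0.081 | Worsening |
| 11112 = 0.848 | blank | 0.919 | +0.071 | Improvement |
| 11121 = 0.796 | 11191 (pain missing) | 0.919 | +0.123 | Improvement |
| 21121 = 0.727 | 21191 (pain missing) | 0.850 | +0.123 | Improvement |

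In the last row, the value returned is a legitimate table entry, so a check for impossible values would not find it. If all 64 planned subjects (SAP 1.3) contributed an index, one misclassified subject would move a responder proportion by 1/64, about 1.6 percentage points.

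**Step 5: check the fix.** With 9 recoded to `.` before scoring, all 781 incomplete patterns give a missing index and the 243 complete states are unchanged.

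**The case against.** The intention is not in doubt. Section 8.5.2 and Appendix 3 both say that an incomplete form has no index, and the last line of the code exists to enforce this. Section 8 names EQ-5D among the patient-reported outcomes and sets out-of-range responses to missing, which gives a programmer grounds to convert 9. The code also needs particular variable names and an input dataset, so some data preparation comes first, and a `.` convention may be applied at that stage. The documents do not show how the analysis dataset is coded.

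Much of this stands, and it makes the error conditional. It does not close the gap. The section 8 rule gives way where something else is specified, and Table 8-4 specifies 9. Item 37 defines range by tables that have no EQ-5D row. A 9 is also an assigned code rather than a response. The recode has to be inferred.

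A reader might infer that every missing item costs 0.081. It does not: the constant applies once per form and is an extra deduction in only 31 of the 781 patterns. A reader might also infer that the EQ VAS code of 999 (SAP 8.5.3) would enter a mean on the 0 to 100 scale. The documents print no EQ VAS scoring code, so no error is shown there.

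**Conclusion.** The inconsistency between the SAP's text and its code is real. Run as printed on data coded per Table 8-4, the code gives every incomplete form an index, contrary to sections 8.5.2 and Appendix 3. The unanswered item is scored as level 1; where nothing else is reported as a problem, the result is 0.919, outside the value set.

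This rests on one assumption, that 9-coded items reach the code without a recode. The documents neither confirm nor exclude it, so they do not support a claim that reported results are wrong. They also give no frequency of missing items, so the examples show a mechanism and not an expected bias.

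The reach is limited to the EQ-5D index summaries and the 0.07 responder analysis, which are descriptive and carry no inferential statistics. EQ-5D is not among the SAP's primary or secondary efficacy endpoints, and the primary endpoint is unaffected. Severity: minor.

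**What to change.** In SAP Appendix 5, immediately before the item 38 code, set any EQ-5D dimension not equal to 1, 2 or 3 (including 9) to `.`. Extending the code's final missing test to include 9 would deal with the Table 8-4 code equally well. Add EQ-5D rows to the range table in item 37 so that the general rule in section 8 visibly covers this instrument.

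As a precaution only, also state that an EQ VAS of 999 is set to `.` before any summary.

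The cost is about two lines of code and a short SAP edit. No new data or change of method is needed, and the index for complete forms does not change.
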